8.2.2. Assessment of self-injection

Analysis with respect to a comparison of the doses administered by the principal investigator or sub-investigator up through Treatment Week 24 and the self-injections performed after Treatment Week 24

The doses administered by the principal investigator or sub-investigator up through Treatment Week 24 and the self-injections performed after Treatment Week 24 will be analyzed using the same method[Section 8.2.1] as for the WOMAC pain subscale score.

These analysis will be summarized based on the self-injection population.

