8.3 Dosage and Administration

(1) MT-5547 and MT-5547 placebos

Assigned investigational drug or comparative drug will be administered subcutaneously every 4 weeks between Week 0 and Week 44*.

MT-5547 1 mg q4w group: MT-5547 1 mg q4w from Week 0 to Week 44

MT-5547 1 mg q8w group: MT-5547 1 mg q8w on Weeks 0, 8, 16, 24, 32, and 40, and MT-5547 placebo q8w on Weeks 4, 12, 20, 28, 36, and 44

MT-5547 placebo group: MT-5547 placebo q4w from Week 0 to Week 44

* All patients previously randomized to 3 mg q4w or 6 mg q8w group under the previous versions of this protocol (up to Ver. 03.00.00000) will be discontinued from study drug immediately and will continue all tests/observations in the post-treatment observation period (ref. 9.1.1 Test/Observation Schedule (2)).

The entire contents of a single prefilled syringe will be injected subcutaneously into the abdomen, thigh or upper arm for each dose. Subjects will be monitored at the study site for 30 minutes after the administration of the investigational drug or comparative drug. The investigational drug or comparative drug study drug will be administered at the scheduled administration days plus or minus 7 days. If the investigational drug or comparative drug cannot be administered during this time window, then the dose will be skipped and study drug will not be administered until the next scheduled treatment date. The investigational drug or comparative drug will be administered after all of the procedures planned for the day of the study visit have been completed.

Furthermore, for subjects who consent to self-inject, the study drug will be administered by self-injection subcutaneously at the study site from Week 24 on. The injection site of self-inject subcutaneously should be the abdomen or thigh, not injected on upper arm.

Precautions Related to the Dosage and Administration

Treatment will be initiated by the baseline day, after all of the tests and observations have been completed, it has been confirmed based on the IWRS that the subject is eligible to participate in the study, and a drug number has been assigned. The investigational drug or comparative drug will be administered once all of the planned procedures on the visit day have been completed.

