In addition, a comparison of the doses administered by (sub)investigator up through Treatment Week 24 and the self-injections performed after Treatment Week 24 and a comparison of the doses administered by (sub)investigator after Treatment Week 24 and the self-injections performed after Treatment Week 24 in subjects who received at least one self-injection after Treatment Week 24 will be included in the statistical analysis of the efficacy and safety data obtained from screening through the post-treatment observation period 20 weeks after the end of treatment period.

In response to the protocol amendment (Ver. 04.00.00000) with removal of 3 mg q4w / 6 mg q8w groups and addition of 1 mg q8w, analysis will be performed as follows; For evaluation on 1 mg q4w, since subjects are randomized to 1 mg q4w / placebo at the same time with the same ratio of 1:1 regardless of pre- or post- amendment, analyses will be performed with pooled comparable data including pre- and post- amendment data on 1 mg q4w / placebo. For evaluation on 1 mg q8w, analyses will be performed with only the post-amendment data.

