5. ANALYSIS POPULATIONS

The analysis of efficacy will be performed in the full analysis set (FAS). The principal analysis set for efficacy will be the modified FAS (mFAS). The analysis of safety will be performed in the safety analysis set (SAF). The analysis of pharmacokinetics will be performed in the pharmacokinetic analysis set.

The analysis sets are defined below. For the contents of the data review meeting, refer to a separate materials.

(1) Efficacy analysis sets

1) Randomized subjects (RAND)

2) FAS

The FAS will consist of all randomized subjects except for the following subjects.

- Subjects who have not received study drug even once
- Subjects with no WOMAC pain subscale score (the primary endpoint) at baseline
- Subjects with no WOMAC pain subscale score (the primary endpoint) at any time point after randomization

3) Modified FAS (mFAS)

The mFAS will consist of the FAS, except for the following subjects.

- Subjects who are randomized to 3 mg q4w group
- Subjects who are randomized to 6 mg q8w group

(2) SAF

The SAF will consist of all randomized subjects except for the following subjects

- Subjects who did not receive study drug even once
- Subjects for whom absolutely no post-randomization safety data are available

(3) Self-injection analysis set(SIAS)

The self-injection analysis set will consist of the mFAS, except for the following subjects.

- Subjects who never performed self-injection

(4) Pharmacokinetic analysis set (PK)

The pharmacokinetic analysis set will consist of subjects who have received investigational drug at least once and who had at least one non-missing post-dose serum drug concentration data.

(5) Anti-drug antibody (ADA) analysis set (ADA)

The ADA analysis set will consist of all treated subjects who received investigational drug or comparative drug at least once and who had at least one non-missing post-dose ADA result.

(6) Neutralizing anti-drug antibody (NAb) analysis set (NAb)

The NAb population includes all treated patients who received any amount of study treatment (drug or placebo; Safety Analysis Set), and either tested negative for ADA or tested positive for ADA with at least one non-missing NAb result (either "NAb negative" or "NAb positive") following the first dose of study drug or placebo.

(7) Concentration-Response analysis set (CR)

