6. STATISTICAL CONSIDERATIONS

6.1. Descriptive Statistics

(1) Non-PK related

Continuous data will be summarized descriptively using the number in the analysis set (N), the number of observations (n), mean, standard deviation (SD), median, minimum and maximum. Categorical data will be summarized using frequency counts and percentages. The denominator for the percentages will be the total number of subjects in the treatment group and analysis population being presented, unless otherwise specified.

(2) PK related

Serum concentrations will be summarized descriptively using N, n, mean, SD, median, Q1, Q3, minimum and maximum by clinical study day (as defined in the protocol) and treatment group.

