Incidence rate ratio estimates and 2-sided 95% confidence interval will be computed using Generalized Estimating Equations with a log-linked Poisson model via the PROC GENMOD procedure if there are events in the placebo group. The model will specify the use of a Poisson probability distribution with an offset= log (patient-observation period days) and model terms for treatment-as-received and each randomization strata. If there is no event in the placebo group, incidence rate ratio will not be calculated and confidence intervals for the incidence rate difference will be computed using Wald method.

The incidence rate estimates for each arm, the estimates of the incidence rate ratio and incidence rate difference between MT-5547 and placebo will be summarized.

The SAS code planned for the analysis is outlined below.

[REDACTED]

Assessment of self-injection

— Analysis with respect to a comparison of the doses administered by the principal investigator or sub-investigator after treatment week 24 and the self-injections performed after treatment week 24

This analysis will be summarized using the data after treatment week 24 by the principal investigator or sub-investigator and the self-injections and by MT-5547 treatment group excluding MT-5547 3mg q4w and MT-5547 6mg q8w on SAF population.

Overall summary for the following will be conducted.

- Subjects with at least one TEAE
- Subjects with at least one adverse drug reaction
- Subjects with at least one TESAE
- Subjects with at least one serious adverse drug reaction
- Subjects with at least one AESI
- Subjects with at least one severe TEAE
- Subjects with at least one TEAE leading to discontinuation of study drug
- Subjects with TEAE leading to death
- Subjects with at least one abnormal NCS or CS for injection site assessment

The following summaries also will be conducted.

- TEAEs by SOC and PT

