10. CHANGE FROM THE PROTOCOL

There are currently no changes to analysis from protocol.

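### In the Week 68 SAP, the efficacy assessment of self-injection cannot be separated from time on treatment, and the safety assessment lacks an at-risk denominator for each injection mode

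*SAP*

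**What the plan says.** **Efficacy.** Week 68 SAP 8.2.2: "The doses administered by the principal investigator or sub-investigator up through Treatment Week 24 and the self-injections performed after Treatment Week 24 will be analyzed". The method is the one that 8.2.1 gives for WOMAC pain. On the population it adds: "These analysis will be summarized based on the self-injection population". Section 5 defines that set as the mFAS without "Subjects who never performed self-injection".

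**How subjects come to self-inject.** Protocol 8.3: "for subjects who consent to self-inject, the study drug will be administered by self-injection subcutaneously at the study site from Week 24 on". Protocol 4.6 adds that the consent form goes only to subjects whom the investigator judges able to do it.

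**Safety.** Week 68 SAP 8.3.1: "This analysis will be summarized using the data after treatment week 24 by the principal investigator or sub-investigator and the self-injections", by MT-5547 group, on the safety set without the 3 mg q4w and 6 mg q8w groups. The general rule in 6.1 is: "The denominator for the percentages will be the total number of subjects in the treatment group and analysis population being presented". That sentence allows exceptions where stated; 8.3.1 states none.

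**Protocol.** The introduction to section 13 lists two comparisons for the efficacy and safety data: investigator doses up to Week 24 against later self-injections, and investigator doses after Week 24 against self-injections after Week 24. The second is followed by the words "in subjects who received at least one self-injection after Treatment Week 24".

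**Declared changes.** Week 68 SAP section 10: "There are currently no changes to analysis from protocol".

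**The concern.** In 8.2.2, knowing the period tells you the mode, and the reverse. Onset of effect, drift over time, adaptation to rescue medication and self-injection would all appear in the same contrast. The placebo self-injectors in the set are not a clean control for time, because the placebo group starts naproxen at Week 16, inside the investigator-dosed period.

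In 8.3.1 the two modes cover the same calendar span, which is sound. The difficulty is who is counted. A subject who left before Week 24 stays in the safety set but received no injection by either mode in the window and cannot contribute an event to either column. There is also no rule for a subject dosed by both modes.

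At stake is whether the report can say anything about self-administration. A reader of these tables could draw a conclusion about mode of injection that the layout cannot carry, in either direction.

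**Working it through.** **1. The plan's own count.** Doses run every 4 weeks from Week 0 to Week 44: 44/4 + 1 = 12. Those from Week 24 on (24, 28, 32, 36, 40, 44) number 6, which agrees with the self-injection categories 1 to 6 in SAP 7.1.1.4. Taken strictly after Week 24 there are 5, so the side on which a Week 24 self-injection falls is not settled. The documents give no sample size or effect size for this assessment.

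**2. The model in 8.2.1.** Its terms are treatment group, time point, their interaction, K-L grade, joint, baseline, and baseline by time point. There is no term for injection mode. Within the self-injection set, a mode comparison from this model is a comparison of earlier with later visits.

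**3. Simulation, true effect of self-injection zero.** Assumptions: 324 subjects (182 + 142, the two 1 mg targets), half self-injecting, between-subject SD 1.8, residual SD 1.2.

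| Assumed shift after Week 24 | Before/after (8.2.2 structure) | Concurrent, no selection | Concurrent, better responders choose self-injection |
|---|---|---|---|
| 0 | 0.01 | 0.00 | -1.38 |
| -0.3 | -0.30 | 0.00 | -1.39 |
| -0.6 | -0.60 | 0.00 | -1.38 |

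The before/after contrast returns the whole time shift. A concurrent contrast does not, but it is open to self-selection; the -1.4 reflects the strength of selection assumed.

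**4. Protocol section 13 against the SAP.**

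| Comparison | Protocol 13 | Week 68 SAP |
|---|---|---|
| Before/after, efficacy | listed | 8.2.2, self-injection set |
| Concurrent, efficacy | listed | absent |
| Before/after, safety | listed | absent |
| Concurrent, safety | listed | 8.3.1, safety set, not limited to self-injectors |

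**5. Denominator in 8.3.1.** Let p be the true post-Week-24 incidence in both modes, r the fraction still on drug at Week 24, and u the fraction of those who self-inject, with one mode per subject. All values are assumptions; the documents give no dropout rate to Week 24.

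- Dilution overall, p × r with p = 0.30: r = 0.90, 0.85, 0.80, 0.75 gives 27.0%, 25.5%, 24.0%, 22.5%.
- Whole arm as denominator, p × r × u for self-injection and p × r × (1 - u) for investigator. With p = 0.40 and u = 0.5: 0.40 × 0.85 × 0.5 = 17% in both columns, or 0.40 × 0.75 × 0.5 = 15% in both. With u = 0.3 and r = 0.85: 0.40 × 0.85 × 0.3 = 10.2% against 0.40 × 0.85 × 0.7 = 23.8%. The columns then follow uptake although the risk is equal.
- If subjects who left were put in the investigator column, its rate would be p × r × (1 - u) / (1 - r × u): 0.17/0.575 = 30% or 0.15/0.625 = 24%, against 40% for self-injection.

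**6. Subjects dosed by both modes.** With an assumed event rate of 0.10 per 4-week interval and 6 doses, incidence by mode is 1 - exp(-0.10 × doses by that mode). If 30% of doses are self-injected this is 16.5% against 34.3%; at 50%, 25.9% in both; at 80%, 38.1% against 11.3%. The rate is the same throughout, so an attribution rule matters.

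**The case against.** - The protocol itself prescribes the before/after comparison, so 8.2.2 implements what was planned. This stands for that comparison; it does not supply the concurrent one.
- The protocol sentence could be read as giving one comparison to efficacy and the other to safety, and the restriction to self-injectors could cover one comparison or both. The wording does not settle either. A firm claim that the SAP breaks the restriction would go too far; that the documents need reconciling does not.
- A reader might infer that the safety comparison is also confounded with time on treatment. It is not: both modes are taken after Week 24 only.
- A reader might infer that dropout before Week 24 biases the efficacy contrast. The same subjects supply both periods, so it limits who the result applies to and does not create a difference between periods.
- A reader might infer that self-injection is bound to look better because the early weeks contain onset of effect. The model reports by visit, nothing says the early visits are averaged, and the code is not in the public text. The direction is unknown.
- A reader might take the 10 to 16 point gap in step 5 (40% against 30% or 24%) as a finding. It needs subjects who left to be placed in the investigator column, which the SAP does not say. With the whole arm as denominator and half self-injecting, the gap is zero.
- A concurrent efficacy comparison brings in selection by consent and by the investigator's judgement, and adjustment will not remove it fully. This stands and must be stated with the result.

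**Conclusion.** The point holds in limited form. For efficacy, mode and time on treatment are aligned by construction in 8.2.2, so the result cannot be attributed to self-injection, whatever its sign. The concurrent efficacy comparison listed in protocol section 13 is missing. For safety, the comparison is concurrent, but the default denominator dilutes the percentages and lets the columns partly follow uptake of each mode. The protocol's restriction to self-injectors, of ambiguous scope, is not carried over, and section 10 declares no change.

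The structural conclusions rest on the text alone. The sizes do not: the 30% and 40% event rates, the 30% and 50% uptake, the 10% to 25% loss and the time shifts are assumptions, and the size and direction of any bias between modes depend on them. The documents do not state that these tables are meant to support a claim about self-administration. SAP 6.2 rules out formal tests and the Week 16 primary analysis is untouched, so the importance is low.

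**What to change.** 1. In 8.2.2, keep the before/after table as descriptive and label it as confounded with time on treatment. Add a concurrent comparison by mode of WOMAC pain at Weeks 28 to 48, among MT-5547 subjects still on study drug at Week 24, adjusted for the Week 24 score, baseline, K-L grade and joint. Label it non-randomised and open to selection by consent and investigator judgement. Confirm that the Week 24 score is available: SAP 9.3 reports it, but the visit list in protocol 9.2.3.1.1 omits Week 24.
2. In 8.3.1, use as denominator for each column the subjects with at least one injection of that mode at or after Week 24. Give a rule for attributing events in subjects dosed by both modes, and say where a Week 24 self-injection belongs.
3. Reconcile 8.2.2 and 8.3.1 with protocol section 13, including the scope of the restriction to self-injectors, and record the differences in section 10.

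The cost is SAP text, one additional model and one re-specified table on data already collected. The added efficacy comparison remains observational.

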8.3. Safety Assessments

Safety assessments will be made on the SAF population.

8.3.1. Adverse Events

Overall summary of TEAEs / Post-treatment AEs for the following will be conducted.

- Subjects with at least one AE
- Subjects with at least one adverse drug reaction
- Subjects with at least one SAE
- Subjects with at least one serious adverse drug reaction
- Subjects with at least one AESI
- Subjects with at least one severe AE
- Subjects with at least one AE leading to discontinuation of study drug
- Subjects with AE leading to death

The following summaries also will be conducted.

- TEAEs / Post-treatment AEs by SOC and PT
- TEAEs / Post-treatment AEs related to drug reactions by SOC and PT
- TEAESI / Post-treatment AESI by SOC and PT
- TESAEs / Post-treatment SAEs by SOC and PT
- TESAEs related to drug reactions by SOC and PT
- TEAEs leading to discontinuation of study drug by SOC and PT

- TEAEs / Post-treatment AEs by SOC, PT and severity
- TEAEs related to drug reactions by SOC, PT and severity
- TEAEs by SOC, PT and relationship to study drug
- TESAEs by SOC, PT and relationship to study drug
- Identified TEAEs / Post-Treatment AEs by SMQ, HLGT, HLT and PT

Each of the summaries will be done by treatment group and combined MT-5547 at the subject level - multiple occurrences of the same event within a subject will be counted once in the summaries by SOC and PT; multiple occurrences of the same event within a subject will be counted once in the maximum severity category (severe > moderate > mild) and/or maximum drug relationship category (reasonable possibility/no reasonable possibility) and/or the earliest duration.

The following will be listed.

- AE
- AESI
- AE leading to discontinuation of study drug
- SAE
- Death
- Joint replacements

adjudicated arthropathy

The number and percentage of patients with images requiring adjudicated arthropathy as well as the number and percentage of those patients with confirmed adjudicated arthropathy including all available follow-up data after baseline will be summarized by treatment group and combined MT-5547. Subtypes of AAs and outcomes of AAs will also be summarized. Time to event with AA will be analyzed using Kaplan-Meir approach and will be plotted by treatment group. Cox regression model will be used for descriptively comparing each treatment group to placebo by obtaining hazard ratio estimates along with 95% confidence intervals.

Incidence of AA will be summarized by treatment group and combined MT-5547.

Incidence rate ratio estimates and 2-sided 95% confidence interval will be computed using Generalized Estimating Equations with a log-linked Poisson model via the PROC GENMOD procedure if there are events in the placebo group. The model will specify the use of a Poisson probability distribution with an offset= log (patient-observation period days) and model terms for treatment-as-received and each randomization strata. If there is no event in the placebo group, incidence rate ratio will not be calculated and confidence intervals for the incidence rate difference will be computed using Wald method.

The incidence rate estimates for each arm, the estimates of the incidence rate ratio and incidence rate difference between MT-5547 and placebo will be summarized.

The SAS code planned for the analysis is outlined below.

[REDACTED]

Assessment of self-injection

— Analysis with respect to a comparison of the doses administered by the principal investigator or sub-investigator after treatment week 24 and the self-injections performed after treatment week 24

This analysis will be summarized using the data after treatment week 24 by the principal investigator or sub-investigator and the self-injections and by MT-5547 treatment group excluding MT-5547 3mg q4w and MT-5547 6mg q8w on SAF population.

Overall summary for the following will be conducted.

- Subjects with at least one TEAE
- Subjects with at least one adverse drug reaction
- Subjects with at least one TESAE
- Subjects with at least one serious adverse drug reaction
- Subjects with at least one AESI
- Subjects with at least one severe TEAE
- Subjects with at least one TEAE leading to discontinuation of study drug
- Subjects with TEAE leading to death
- Subjects with at least one abnormal NCS or CS for injection site assessment

The following summaries also will be conducted.

- TEAEs by SOC and PT

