For patients with events, number of patient years is calculated up to the date of the first event and for patients without event, it corresponds to the length of the study observation period.

Incidence Rate will be calculated using the formula.

Incidence Rate = the number of patients with event × 100 / sum of observation periods for all patients (days) × 365.25*

* 1 year = 365.25 days

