8.3.13. Joint Replacement

Number and percentage of patients with joint replacement including all available follow-up data after baseline will be summarized by treatment group and combined MT-5547. Time to event with joint replacement including all available follow-up data after baseline will be analyzed using Kaplan-Meir approach and will be plotted by treatment group.

All data will be listed.

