9.2. Treatments to Report

Treatment	For TFLs
MT-5547 1 mg q8w	MT-5547 1 mg q8w
MT-5547 1 mg q4w	MT-5547 1 mg q4w
MT-5547 1 mg q4w and MT-5547 1 mg q8w	MT-5547 Combined
MT-5547 3 mg q4w	MT-5547 3 mg q4w
MT-5547 6 mg q8w	MT-5547 6 mg q8w
Placebo	Placebo
Placebo group and all active dose levels	Total

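### Most Week 68 adverse event tables give only crude percentages, although the stopped 3 mg q4w and 6 mg q8w arms have shorter on-treatment windows than the continuing arms, so a dose-related excess can be understated or appear reversed.

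*SAP*

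**What the plan says.** **Who is in the tables.** Safety is analysed on the SAF (Week 68 SAP 8.3). Section 5 defines it: "The SAF will consist of all randomized subjects except for the following subjects", the exceptions being subjects never dosed and subjects without any safety data. The 3 mg q4w and 6 mg q8w arms therefore stay in, and section 9.2 lists both among the reported treatments. The only adverse event summary in 8.3.1 that leaves them out is the self-injection comparison.

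**How long they were treated.** Under Protocol 8.3 the patients in these two arms "will be discontinued from study drug immediately and will continue all tests/observations in the post-treatment observation period". The continuing arms are dosed from Week 0 to Week 44.

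**What is counted.** The tables in 8.3.1 count subjects with at least one event: "Each of the summaries will be done by treatment group and combined MT-5547 at the subject level". Section 6.1 sets the denominator: "The denominator for the percentages will be the total number of subjects in the treatment group" and analysis population. A treatment-emergent event must fall in the on-treatment period, which ends 28 days after the last dose (7.1.3 and 7.1.3.1 (1)).

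**Where follow-up time enters.** Section 7.1.3.1 (7) defines a rate per 100 patient-years. For a patient without an event, "it corresponds to the length of the study observation period". Section 8 uses this rate only for adjudicated arthropathy, which also gets Kaplan-Meier, Cox and Poisson analyses (8.3.1, 8.3.8). For joint replacement, 8.3.13 says "Number and percentage of patients with joint replacement including all available follow-up data after baseline will be summarized" and adds a Kaplan-Meier analysis, but no rate, ratio or interval.

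**The concern.** A percentage of subjects with an event grows with the time at risk. Putting such percentages side by side is fair when the windows are similar. Here they differ by arm: two arms lost their dosing at the amendment and the others were planned to run to 48 weeks.

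The events affected matter for this drug. According to the background section of the protocol, the data monitoring committee's recommendation to stop the higher doses rested on joint replacement, peripheral edema, arthralgia and a trend in early fractures. The Week 68 SAP forms arthralgia-related and fracture-related groups (7.1.3.1 (5)) but tabulates them as subject counts and percentages. A reader who compares doses down a row could conclude that the higher doses carried less risk when the rate was in fact higher.

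**Working it through.** **1. The 48 weeks.** Week 68 SAP 7.1.1.4: duration = last injection − first injection + 28. With the last injection at Week 44 (Day 309) and the first on Day 1: 309 − 1 + 28 = 336 days = 48.0 weeks. The stated treatment period reproduces.

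**2. When the direction reverses.** Let the continuing arm have rate λ over 48 weeks and the stopped arm rate Rλ over T weeks on treatment. The crude percentages are 1 − exp(−48λ) and 1 − exp(−RλT). The stopped arm shows the smaller figure when RT < 48, that is R < 48/T.

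| T (weeks, assumed) | Rate ratio below which the stopped arm looks safer |
|---|---|
| 8 | 6 |
| 12 | 4 |
| 16 | 3 |
| 24 | 2 |
| 32 | 1.5 |

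**3. An illustration.** Assume 20 events per 100 patient-years in a stopped arm and 10 in a continuing arm. Crude percentage = 1 − exp(−rate × weeks/52.18).

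| T | Stopped arm | Continuing arm, 48 weeks |
|---|---|---|
| 8 | 3.0% | 8.8% |
| 12 | 4.5% | 8.8% |
| 24 | 8.8% | 8.8% |
| 32 | 11.5% | 8.8% |

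A doubled rate looks roughly halved at 12 weeks, vanishes at 24, and is visible but understated at 32.

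**4. If events come early.** Let the hazard be three times higher in the first 16 weeks. Cumulative hazard over 48 weeks is then 3 × 16 + 32 = 80 units; over T = 8, 12, 16 and 24 it is 24, 36, 48 and 56. The thresholds fall to 80/24 = 3.3, 80/36 = 2.2, 1.7 and 1.4. A true doubling is still reversed at 12 weeks, but not at 16.

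**5. Post-treatment tables.** Completers: Day 477 − Day 337 = 140 days. Stopped subjects are followed for 24 weeks from the last dose, of which 28 days count as on-treatment: 168 − 28 = 140 days. The planned windows are equal, so these tables are not affected.

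**6. Joint replacement.** This uses all follow-up, so the comparison is T + 20 weeks against 68. With the rates of step 3 and T = 12, the crude percentages are 11.5% (32 weeks) and 12.2% (68 weeks); at T = 16 they are 12.9% and 12.2%. The distortion is much smaller than for TEAEs.

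**7. Does the existing rate definition repair the TEAE tables?** Its denominator for event-free patients is the whole observation period, T + 20 weeks, while the TEAE numerator stops at T. The rate is p / [p/λ + (1 − p) × 20/52.18], with p the crude proportion and λ here the arm's own yearly rate.

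- Stopped arm, T = 12: 0.0450 / (0.2248 + 0.3661) = 7.6 per 100 patient-years.
- Stopped arm, T = 8: 0.0302 / (0.1510 + 0.3717) = 5.8.
- Continuing arm: 0.0879 / (0.8789 + 0.3496) = 7.2.

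The true ratio of 2 becomes about 1.06 at 12 weeks and 0.81 at 8 weeks, still reversed. On-treatment person-time returns 20 and 10 at every T.

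**The case against.** The strongest reply is that the plan already contains several safeguards, and most of it stands.

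- **Joint replacement.** A reader might infer that it has no allowance for follow-up. It does: the planned Kaplan-Meier analysis censors unequal follow-up. Only an effect estimate and an interval are missing.
- **Pooled columns.** The Combined column is "MT-5547 1 mg q4w and MT-5547 1 mg q8w", so the stopped arms do not dilute it. Section 9.2 also lists a Total ("Placebo group and all active dose levels"), and a reader might infer that it appears in the event tables. Section 8.3.1 plans only treatment groups and Combined; where the SAP wants an overall column, as for disposition and demographics, it says so.
- **Week 16 tables.** The Week 16 SAP tabulates TEAEs, serious TEAEs and AESIs by arm on the SAF and leaves out events after the Week 16 dose, which caps every arm near 16 weeks. The same illustration gives 3.0% v 3.0% at T = 8, 4.5% v 3.0% at T = 12 and 5.9% v 3.0% from T = 16: no reversal. This is partial relief. Those tables omit the identified-event groups and joint replacement, and a doubling still disappears at T = 8.
- **Duration table.** Treatment duration by arm is tabulated (8.1.8). It reveals the imbalance but corrects no percentage.
- **Purpose.** The Week 68 analysis runs no formal tests, its stated aim is the two 1 mg regimens against placebo, and the signal that closed the higher doses came from another study, R475-PN-1523. These limit the consequence. They do not make the percentages comparable.

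**Conclusion.** The point holds for the Week 68 TEAE, SAE, AESI (other than arthropathy) and identified-event tables. They set crude percentages over unequal on-treatment windows next to each other, and under a constant hazard an excess is reversed when the rate ratio is below 48/T.

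The size rests on assumptions. The documents do not give the exposure reached in the stopped arms, the event rates are illustrative, and the timing of events is unknown. A reader might infer that the tables will show a reversed dose pattern, or will contradict the decision to stop the higher doses. The documents do not support that: at 32 weeks on treatment a doubling keeps its direction, and early events lower the threshold.

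The efficacy conclusion is not touched. This is a minor, inexpensive improvement in reporting.

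**What to change.** **TEAE, SAE, AESI and identified-event summaries (Week 68 SAP 8.3.1).** In every arm, add the rate per 100 patient-years with an exact 95% confidence interval. Count person-time from first dose to the earlier of the first event and 28 days after the last dose, so that numerator and denominator cover the same period. Do not carry the 7.1.3.1 (7) denominator over unchanged (step 7).

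**Joint replacement (8.3.13).** It uses all follow-up, so the 7.1.3.1 (7) rate fits. Add it with a 95% confidence interval, and add the Cox hazard ratio with 95% confidence interval that is already planned for arthropathy.

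No change to a Total column is needed.

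**Cost.** A few more columns, largely from code already planned, and no new data. Intervals in the stopped arms will be wide: 57 patients for an assumed 12 weeks give 57 × 12/52.18 = 13.1 patient-years, or about 2.6 expected events at 20 per 100 patient-years. The size of these arms also needs reconciling. Section 3.3 gives 57 in each, which makes 506 + 114 = 620, but its stated total of 563 equals 506 + 57.
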